#### **Protocol Numbers**

CCRC D14007  
CPHS 28499  
*Version Date Modification(s)*

Version History			
V1	6/16/2015		Initial submission
V2	10/23/2015		Update information regarding tumor stage for inclusion criteria, remove platelet count and ANC from inclusion criteria, Co-I changes
V3	3/7/2016		Clarification of study procedures, update to specify that tumors can be benign
V4	1/19/2017		PI change, expansion of Phase 1A and 1B cohorts (justification, results for 6 Patient 1A patients), Increase implant duration to 52 weeks (justification), increase tumor location to 3 cm to skin surface
V5	3/29/2017		Add ultrasound to OxyChip implantation procedure
V6	8/28/2017		Clarification of study procedures, clarification of eligibility (no concurrent enrollment in other clinical research studies, add platelet count and ANC to exclusion criteria), details added about OxyChip storage
V7	5/7/ 2018		Add ultrasound to EPR measurements
V7.1	7/10/2018		Co-I changes
V8	10/10/19		Co-I changes, evaluation points in Phase 1B updated, adding information on adding fiducials to OxyChips and OxyChip removal, inclusion criteria revised to include minimum tumor size

**List of Abbreviations**

BOLD MRI	-	blood oxygen level-dependent MRI
CCRC	-	Clinical Cancer Review Committee
CO 2	-	carbon dioxide
CPHS	-	Committee for the Protection of Human Subjects (Dartmouth's IRB used by DHMC)
CRF	-	case report form
CT	-	computerized tomography
DHMC	-	Dartmouth-Hitchcock Medical Center
DSMAC	-	Data Safety Monitoring and Accrual Committee
DWI	-	diffusion-weighted imaging
EPR	-	electron paramagnetic resonance
FDA	-	Food and Drug Administration (US Dept of Health and Human Services)
FTIR	-	Fourier transform infrared spectroscopy
GC-MS	-	Gas chromatography - mass spectrometry
GHz	-	gigahertz
Gy	-	gray
HIF-1alpha	-	hypoxia-inducible factor-1 alpha
HIPAA	-	Health Insurance Portability and Accountability Act of 1996
ICP-MS	-	Inductively coupled plasma – mass spectrometry
LiNc	-	lithium naphthalocyanine
LiNc-BuO	-	lithium octa- n -butoxynaphthalocyanine
LiPc	-	lithium phthalocyanine
MRI	-	magnetic resonance imaging
MHz	-	megahertz
NCCC	-	Norris Cotton Cancer Center
NIR	-	near-infrared
NMR	-	nuclear magnetic resonance
O 2	-	molecular oxygen
OxyChip	-	oxygen-sensing probe made by embedding LiNc-BuO in PDMS
PDMS	-	polydimethylsiloxane
PHI	-	patient health information
pO 2	-	partial pressure of oxygen
UADE	-	unanticipated adverse device effect

## Study Summary

Title	A Single-Institutional, Phase I Trial of Repeated Oxygen Measurements in Subcutaneous Tumors by Electron Paramagnetic Resonance (EPR) Oximetry using an Implantable Oxygen Sensor (OxyChip)
Short Title	EPR Oximetry using OxyChip
Protocol Number	D14007, CPHS 28499
Phase	First-in-humans, early feasibility study for OxyChip implantation with subsequent expansion to a larger Phase I trial. Phases: 1A (tumor with planned surgical resection only and consequently with an expected duration of implantation for up to 4 weeks); and 1B (tumor with neoadjuvant radiation therapy or chemotherapy followed by planned surgical resection, with expected duration of implantation of up to 12 weeks for radiation and 24 weeks or more for chemotherapy.) OxyChip implant duration for both phases can be extended to 52 weeks excluding the first 6 patients enrolled into Phase 1A where implant duration is up to 4 weeks.
Methodology	Phase I (first-in-human, early feasibility trial)
Study Duration	5 years
Study Center(s)	Single institution: Dartmouth-Hitchcock Medical Center (DHMC)
Objectives	Primary: Establishment of safety of OxyChip implantation in humans; Secondary: establishment of feasibility of OxyChip for measurements of oxygen using EPR oximetry in humans.
Number of Subjects	60 total evaluable subjects planned: 3 subjects in Phase1A will be evaluated and reviewed before enrolling another 3 subjects. After completion of the first 6 subjects in Phase 1A, if there are no unacceptable toxicities from the OxyChip, that cohort will be expanded to a total of 30 subjects. Phase 1B will consist of one cohort of 3 subjects receiving chemotherapy and one cohort of 3 subjects receiving radiotherapy. Once a cohort has enrolled 3 subjects and there are no unacceptable toxicities from the OxyChip, the completed cohort will be expanded to enroll additional subjects. No more than 30 subjects will be enrolled in Phase 1B. Phase 1A and Phase 1B will be evaluated separately with regards to this expansion; i.e. , Phase 1A may expand to 30 subjects while Phase 1B is still accruing.
Diagnosis and Main Inclusion Criteria	Tumors, located within 3 cm of skin or mucosal surface AND tumor resection is planned.
Study Product, Dose, Route, Regimen	OxyChip containing lithium octa- n -butoxynaphthalocyanine (LiNc-BuO) oxygen-sensing crystals embedded in polydimethylsiloxane (PDMS) polymer to be used in recording oxygen levels in tumors using EPR oximetry.
Duration of Administration	Implantation time up to 4 weeks for the first six Phase 1A patients, but $\leq$ 52 weeks for the additional 24 patients. The duration of the course of radiation therapy or neoadjuvant chemotherapy for phase 1B patients, but $\leq$ 52 weeks.

Reference therapy	N/A
Statistical Methodology	This is a pilot study designed to (1) test the safety of the OxyChip, (2) test the feasibility of taking EPR measurements repeatedly with the OxyChip, and (3) help design larger studies to evaluate oxygen adaptive therapies. We will proceed by initially enrolling 3 patients in a cohort and evaluate the initial (and each subsequent) cohort of 3 patients for adverse events prior to proceeding to the next cohort. As a secondary goal, we will investigate the feasibility of repeated oxygen measurements using EPR oximetry.

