### 1.5.5 Compliance with FDA and Dartmouth IRB regulation

[figure not shown]
We have obtained approval from the FDA (Investigational Device Exemption) and the Dartmouth IRB (CPHS) to increase the total number of enrollments from the initial cohort of 12 to 60 patients, and to extend

the length of OxyChip residence in the tumor for up to 1 year. Currently, we have completed the Phase 1 safety and efficacy study requirement set by the

to 1 year. Currently, we have completed the Phase 1 safety and efficacy study requirement set by the FDA.

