## 3 Study Design

### 3.1 General Design

This is a Phase 1 clinical trial. Total enrollment will be 60 evaluable patients. Evaluable patients will be defined as patients who have the OxyChip implantation for the minimum of 3 days.

The study is split into Phase 1A (shorter duration of implantation with no other cancer therapy planned prior to excision) and Phase 1B (longer duration of implantation that is typically up to 12 weeks while receiving radiation therapy or longer if receiving neoadjuvant chemotherapy prior to surgical excision), as described below. OxyChip implant duration for both phases can be extended to 52 weeks (excluding the initial 6 evaluable patients in Phase 1A which may have the OxyChip implanted up to 4 weeks).

[figure not shown]
The initial 6 evaluable patients in Phase 1A will have the OxyChip placed for a short duration (up to 4 weeks) after which the OxyChip will be removed when the tumor mass is resected, prior to delivery of any further therapies. After successful implantation and removal of the OxyChip without any unacceptable toxicity in the first 6 evaluable patients, the Phase 1A cohort will be expanded to a total of 30 patients. In order to complete the safety and toxicity assessment of the short-term implantations, we will require that at least 3 patients have OxyChip implantations for a duration of at least 2 weeks, prior to proceeding to Phase 1B (long term implantation). This may require enrollment of additional patients in Phase 1A in order to meet this criterion. Phase 1B will consist of one cohort of 3 evaluable patients receiving chemotherapy treatment and one cohort of 3 evaluable patients receiving radiotherapy. Only after a full evaluation of the first 3 patients that underwent chemotherapy will additional patients receiving chemotherapy be enrolled. Similarly, only after a full evaluation of the first 3 patients that underwent radiotherapy will additional patients receiving radiotherapy be enrolled. The two cohorts of 3 patients in Phase 1B are independent of each other, so either of these cohorts may continue accrual after the initial 3 patients while the other is still accruing for the initial 3 patients. A total of 30 patients will be enrolled in Phase 1B. .

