Patient population	
There will be a total of 30 patients enrolled in Phase 1A.
 
Initially, 3 patients will be enrolled; the OxyChip will be placed; physical examination of the site will be made periodically (at least in conjunction with visits where oxygen measurements will be made) starting from one day following implantation for up to 52 weeks – at which point the tumor will be resected with concurrent removal of the OxyChip. If no adverse events are noted in the physical exams or tissue pathology, an additional 3 patients will be enrolled in this phase of the study. The decision to start the second cohort of 3 will be made by the study PI after review of surgical pathology reports and after the first 3 evaluable patients are at a time point more than 2 weeks following surgical removal of the OxyChip. Next, if no unacceptable toxicity is noted after completion of the first 6 patients, the enrollment will be open to 24 more, for a total of 30 patients. (Note: the enrollment totals will include patients enrolled at DHMC or Emory University, once the addition of Emory as a participating site is approved.)
 
In addition the following eligibility and exclusion criteria will apply:
 
 
• Superficial tumors located <math>\leq 3</math> cm from skin or mucosal surface.
 
• Surgical resection of the tumor is planned at least 3 days following implantation.
 
• Eligible tumors for this phase of the protocol are any tumors that (a) are identified by imaging or physical exam to be superficial enough for OxyChip placement and (b) will receive surgical resection with intent to remove the entire tumor.
 

	
 
• Previous radiation to the site is not allowed.
 
• Planned use of chemotherapy or radiation therapy or use of angiogenesis inhibitor prior to resection is not allowed.
 
• Patients do not have to agree to an oxygen measurement in order to be eligible. Although oxygen measurements are desirable, the primary endpoint is safety of the OxyChip placement and removal over a short time frame.
 
• Tumors must be <math>\geq 2.5</math> cm in minimum diameter to be eligible.
 

OxyChip placement	Placement of OxyChip will be through a minimally invasive procedure (see methods for implantation protocol ).

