OxyChip removal	The OxyChip will be removed at the time of surgical resection, which will occur within 52 weeks from the time of implantation. Surgery date must be at least three days after placement of the OxyChip. Tumor tissue surrounding the implanted device will be collected and examined for adverse events (primary) and stored to allow for future evaluation of molecular biomarkers (exploratory).
Oxygen measurements	The goal is for at least 2 oxygen measurements to be taken in the period between the day of OxyChip placement and removal (secondary objective). Note, however, that oxygen measurements are not necessary to determine the presence or absence of any unexpected adverse device events of implanting the OxyChip, for the study's primary goal.

PHASE 1B	
Purpose	
Primary: Safety of the OxyChip during neoadjuvant radiotherapy or neoadjuvant chemotherapy with planned surgical resection as part of standard oncologic therapy.
 
Secondary: Feasibility of oxygen measurements during neoadjuvant radiotherapy or neoadjuvant chemotherapy using the OxyChip.

Patient population	
There will be a total of 30 patients enrolled in Phase 1B.
 
Phase 1B will consist of one cohort of 3 evaluable patients receiving chemotherapy treatment and one cohort of 3 evaluable patients receiving radiotherapy. Only after a full evaluation of the first 3 patients that underwent chemotherapy will additional patients receiving chemotherapy be enrolled. Similarly, only after a full evaluation of the first 3 patients that underwent radiotherapy will additional patients receiving radiotherapy be enrolled. The decision to enroll additional patients in each cohort will be made by the study PI after review of surgical pathology reports and after the 3 evaluable patients are greater than 2 weeks after surgical removal of the OxyChip. The two cohorts of 3 patients in Phase 1B are independent of each other, so either of these cohorts may continue accrual after the initial 3 patients while the other is still accruing for the initial 3 patients.
 
In addition, the following eligibility and exclusion criteria will apply:
 
 
• If a patient is to receive neoadjuvant chemotherapy or radiotherapy at a hospital other than DH prior to resection of the cancer at DH, patients
 

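### Limiting the primary safety analysis to patients implanted for at least 3 days can drop early device- or procedure-related events, and the planned size of 60 is counted in two different units

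*Combined protocol and SAP*

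**What the plan says.** **Analysis population.** Section 7.2 assigns both the primary and the secondary analysis to the evaluable participants. Section 3.1 gives the definition: "Evaluable patients will be defined as patients who have the OxyChip implantation for the minimum of 3 days".

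**Endpoint and early removal.** Section 3.2 makes the primary endpoint all CTCAE toxicities of grade 3 or higher that are attributed to the device or the procedure. The primary objective in 2.1 likewise covers the implantation procedure. Section 4.4.1 allows removal of the chip at any time on request and calls for early removal when there is an adverse event associated with the implant.

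**Size.** The documents state it in two units:

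- Evaluable: "60 total evaluable subjects planned" (Study Summary), and "Total enrollment will be 60 evaluable patients" (3.1).
- Enrolled, Phase 1A: "There will be a total of 30 patients enrolled in Phase 1A" (3.1 schema), reached when "the enrollment will be open to 24 more, for a total of 30 patients".
- Enrolled, Phase 1B: "There will be a total of 30 patients enrolled in Phase 1B" (3.1 schema), and as a ceiling, "No more than 30 subjects will be enrolled in Phase 1B" (Study Summary).
- Approved by the FDA and the IRB (1.5.5): permission to "increase the total number of enrollments from the initial cohort of 12 to 60 patients".

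The documents state no replacement rule for non-evaluable patients and no allowance for loss. Section 7.1 takes the size from a range recommended for early phase I trials. It gives no power calculation.

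**The concern.** A safety denominator should be fixed by exposure, not by what happens afterwards. Here exposure begins when the needle goes in, and the endpoint expressly includes harm from the procedure. Membership of the analysis set, however, depends on the chip staying in for 3 days, and one stated reason for taking it out early is an adverse event linked to the implant. Patients with the most immediate harm are therefore the ones who can leave the analysis. A failed placement with a complication would also be excluded, because that patient has no implantation time.

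This matters because safety is the trial's primary purpose and the expected number of events is very small. When the expected count is zero or one, losing a single patient with an event changes the reported result from some toxicity to none.

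The size statement is a lesser matter. If 30 and 30 count enrolled patients, the maximum enrolled equals the evaluable target, and the two agree only if nobody is lost before day 3.

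**Working it through.** **1. Following one patient through the plan.** Suppose placement causes a grade 3 event that is attributed to the procedure, and the chip is removed on day 2.

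| Section | Effect on this patient |
|---|---|
| 3.2 | The event meets the primary endpoint |
| 4.4.1 | Early removal follows from the event |
| 3.1 | Under 3 days implanted, so not evaluable |
| 7.2 | Not in the primary analysis |
| 8.4 | The event stops the study pending review, whether or not the patient is evaluable |

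The event is seen during conduct. Nothing in 7.2 puts it back into the reported rate.

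**2. What one such event does to the result.** This is an illustration with exact (Clopper-Pearson) two-sided 95% limits. The plan itself specifies no interval.

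| Denominator | Events/n | Rate | Upper limit |
|---|---|---|---|
| All 60 implanted | 1/60 | 1.7% | 8.9% |
| Evaluable only | 0/59 | 0% | 6.1% |
| One phase, all 30 implanted | 1/30 | 3.3% | 17.2% |
| One phase, evaluable only | 0/29 | 0% | 11.9% |

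**3. The plan's own total.** Phase 1A is 3 + 3 + 24 = 30. Adding 30 for Phase 1B gives 60, so the stated figure is reproduced. As a count of enrolled patients it equals the evaluable target exactly, and the margin is 60 − 60 = 0. With k patients lost before day 3, at most 60 − k are evaluable.

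**4. Effect of the size ambiguity on precision.** The documents give no non-evaluable rate, so d is an assumption. The expected number evaluable is 60(1 − d). With zero events the exact two-sided 95% upper limit is 1 − 0.025^(1/n).

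| Assumed d | n evaluable | Upper limit |
|---|---|---|
| 0% | 60 | 6.0% |
| 5% | 57 | 6.3% |
| 10% | 54 | 6.6% |

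**5. If 30 per phase is meant as evaluable.** The enrolment needed per phase is 30/(1 − d), rounded up. At d = 5% this is 31.6, so 32 per phase and 64 in total. At d = 10% it is 33.3, so 34 per phase and 68 in total. Both totals exceed the 60 enrolments that 1.5.5 describes as approved.

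**The case against.** **On the size.** A reader might infer that 60 evaluable patients cannot be reached and that the design fails on its own terms. The documents do not support that:

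- Section 3.1 itself expresses total enrolment in evaluable patients. The document also uses the two words interchangeably for the same groups: the first six in Phase 1A are called enrolled in the Study Summary and evaluable in 3.1. If the totals count evaluable patients, 30 + 30 = 60 and nothing conflicts.
- Only Phase 1B has an explicit ceiling. Phase 1A has a planned total, and 3.1 foresees possible extra Phase 1A patients, although only to satisfy the condition for opening Phase 1B.
- Removal makes a patient non-evaluable only if it happens before day 3. Eligibility (4.1) requires an anticipated interval of at least three days to surgery, and 5.2.4 expects at least 5 weeks in place in Phase 1B. Losses should be few.
- No power is stated, so a shortfall of a few patients misses no stated criterion.

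All of this stands, and it reduces the size question to one of wording. What remains is that the Phase 1B ceiling and the 60 approved enrolments do not sit easily with replacing non-evaluable patients.

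**On the denominator.** A reader might also infer that early events escape oversight. They do not: the stopping rule in 8.4 covers any grade 3 or higher toxicity, and 8.2 records suspected procedure-related effects with no evaluability condition. In addition, section 1.5.6 reports no grade 3 or higher toxicity caused by the chip so far, so there is no sign that the exclusion has yet removed a primary event. These points limit the harm. They do not answer the objection to 7.2, which governs what the final analysis counts.

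**Conclusion.** The point holds for the analysis population. As written, 7.2 permits an outcome-dependent exclusion from the primary safety analysis, and its direction is known: it can only remove early events attributed to the device or the procedure, so it biases the rate downward. Its size depends on how many such patients arise. The documents do not give that number, and section 1.5.1, the account of enrolment to date, was not available to check it. One case is enough to turn 1/60 into 0/59.

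The planned size is ambiguous rather than unattainable. The loss of precision is small, from 6.0% to 6.3% or 6.6% under assumed losses of 5% or 10%. Those rates are illustrative and have no anchor in the documents.

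**What to change.** 1. **Section 7.2.** Analyse the primary safety endpoint in all patients in whom implantation was attempted or completed. Keep the 3-day evaluable set for the feasibility analysis and report its number separately.
2. **Size.** State once, and use throughout, whether 30 and 60 count implanted or evaluable patients. If implanted, say that slightly fewer may be evaluable; no extra enrolment is then needed. If evaluable, add a replacement rule and reconcile it with the Phase 1B ceiling and the 60 approved enrolments in 1.5.5.

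**Cost.** Wording changes in the Study Summary, 1.6.1, 3.1, the schema and 7.2. If implanted patients are counted, the headline evaluable number may be slightly smaller. The safety change needs no new visits or assessments, because adverse effects are already recorded without regard to evaluability.

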# 1 Introduction

This document is a protocol for a human research study. This study is to be conducted according to US and international standards of Good Clinical Practice (International Conference on Harmonization ICH E6), the Code of Federal Regulations Title 21 parts 803 and 812, and other applicable government regulations and Institutional (Dartmouth's Committee for the Protection of Human Subjects, CPHS) research policies and procedures.

## 1.1 Background

Tumor hypoxia (low oxygen levels) confers a poor prognosis and resistance to standard radiotherapy in the treatment of many tumor types. Based on oxygen measurements using polarographic electrode and hypoxia markers, several research groups have shown that tumor hypoxia is a poor prognostic factor; hypoxic tumors are more resistant to radiotherapy and chemotherapy and have increased malignant potential. Oxygen measurements using a polarographic electrode have been performed pre-treatment but are difficult to perform repeatedly during or after treatment to assess tumor or tissue oxygenation. Hypoxia markers (exogenous substances such as misonidazole and pimonidazole, or endogenous markers such as hypoxia-inducible factor-1 alpha (HIF-1 alpha) and carbonic anhydrase IX (CA IX)) are used to visualize hypoxic areas in histological specimens. The histologic methods only provide a static picture of oxygenation which, *in vivo*, is likely to be in constant flux. Knowing the fluctuations in tissue oxygenation may be critical for determining the optimal treatment and the risk of post-treatment complications, thereby optimizing the therapeutic ratio. Such an assessment requires the means to make repeated direct measurements of oxygen in tissue at specific sites, a capability that is not available at present. Thus, there is an unmet need for a device capable of monitoring tumor tissue oxygenation. Achieving this capability would have very significant implications in cancer treatment.

Electron paramagnetic resonance (EPR) oximetry has the potential to fulfill this clinical need. EPR oximetry has been established in both animal models and initial clinical studies at Dartmouth to be a very effective method for measuring oxygen in tissues or tumors directly, repeatedly, and non-invasively following an initial introduction of the paramagnetic EPR reporter material. However, the existing approach for the clinical use of EPR is limited due to the unavailability of a sensitive and reliable oxygen-sensing probe. New oxygen-sensing probes have shown superior characteristics in pre-clinical models, opening up the clinical use of this technology more broadly and importantly to tumors in need of hypoxic monitoring and intervention. We are developing a translational program to apply EPR oximetry more broadly in clinical practice to improve radiation therapy. The first step in this development work is to bring the paramagnetic oxygen-sensing crystals, lithium octa-*n*-butoxynaphthalocyanine (LiNc-BuO), into clinical use.

